After each 2-minute session, participants will be asked whether they had any side effects; if they select no, they will not be asked any further information regarding the tolerability of the current session. If participants indicate that they experienced adverse effects, they will be presented with a list of symptoms from the Visual Discomfort Questionnaire to select the frequency at which each symptom occurred (Vinkers et al., 2024). Any reported side effect will then be rated on a 10-point scale, this will be referred to as the *tolerability score* or symptom discomfort score, the scale ranges from 0 (no symptom discomfort) to 10 (worst possible symptom discomfort), with 3 indicating mild symptom discomfort, 5 moderate symptom discomfort, and >7 severe symptom discomfort. Any report of a scorer >7 will result in that parameter's testing being stopped immediately to avoid further discomfort.

Participants will also report their overall experience on a 0-100 sliding scale via Qualtrics, asking the participant to report how engaging, pleasurable, overall uncomfortable, and sleepy each session was.

After each round of questions, participants will have an opportunity to share their thoughts on the session and also have a break.

To ensure that the experimental procedure has not inadvertently increased participants' depressive symptoms, participants will fill out the M3VAS change and the PHQ-9 again at the end of the testing session. If participants report a deterioration in well-being as indexed by any increase in M3VAS scores in the pre-to-post measurements, support will be offered and the participant referred to relevant sources of support, such as the University of Sussex-specific counselling services for students, as well as their GP, general non-emergency mental health support, or local A&E services, depending on the severity of symptoms.

After the administration of all sessions and questionnaires, participants will be debriefed; this will be the end of the testing session.

B. CRITERIA FOR DISCONTINUING OR MODIFYING ALLOCATED INTERVENTIONS FOR A GIVEN TRIAL PARTICIPANT

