The tolerability score will be used to determine which parameters are appropriate for developing the WP2 intervention. Tolerability scores above 7 indicate severe discomfort due to associated side effects. Strobe light parameters that elicit a tolerability score exceeding 7 with an 80% confidence limit will be considered inappropriate for administration to the MDD population and will not be included in the intervention.

Secondary outcomes:

Secondary outcomes will only be explored through exploratory analyses between sessions and participants, and will include the following measures:

- Type, frequency and intensity of symptoms
- Feasibility, participant recruitment numbers over time
- Participants' report of arousal, enjoyment, overall discomfort and engagement as reported through single items (scale 0-100).

The type, frequency, and intensity of side effects associated with strobe light parameters will provide early insights into potential mild symptoms that strobe light may cause in individuals with MDD, serving as an early indicator for future treatments.

Feasibility does not have direct clinical implications beyond being an estimate of the local population with MDD and general interest in experiencing strobe.

Participants' arousal, enjoyment, overall discomfort and engagement do not have direct clinical implications, but will be analysed to understand trends of participants' experiences during different strobe light parameters and used to inform the development of the intervention in WP2.

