12.1. RATIONALE FOR THE SELECTION OF THE DOMAIN FOR THE TRIAL'S PRIMARY OUTCOME

This study aims to evaluate the safety and tolerability of exposure to stroboscopic light in individuals with MDD and to collect critical data on the stroboscopic parameters that reliably elicit tolerable, comfortable, and engaging experiences.

Tolerability is assessed by participants selecting which side effects they experienced, if any. The potential side effects are drawn from three of the Visual Discomfort Questionnaire's (VDQ) subscales: sickness, eye discomfort and head discomfort (Vinkers et al., 2024). The VDQ was developed to measure the discomfort caused by various visual stimuli. In this study, the subscale for side effects on vision is omitted, as participants will have their eyes closed during the strobe sessions, and visual hallucinations are considered part of the experience. A 10-point scale is used to signify the severity of symptom discomfort, allowing for an immediate understanding of participants' tolerance levels; this measure comprises their tolerability score.

12.2. IF THE ANALYSIS METRIC FOR THE PRIMARY OUTCOME REPRESENTS WITHIN-PARTICIPANT CHANGE, DEFINE AND JUSTIFY THE MINIMAL IMPORTANT CHANGE IN INDIVIDUALS

This does not apply to the current study.

12.3. IF THE OUTCOME DATA COLLECTED ARE CONTINUOUS BUT WILL BE ANALYZED AS CATEGORICAL, SPECIFY THE CUTOFF VALUES TO BE USED

This is not applicable to this research study.

12.4. IF OUTCOME ASSESSMENTS WILL BE PERFORMED AT SEVERAL TIME POINTS AFTER RANDOMIZATION, STATE THE TIME POINTS THAT WILL BE USED FOR ANALYSIS

No randomisation or blinding will take place in this study.

After each 2-minute strobe session participants will answer questions regarding potential side effects, tolerability and their overall stroboscopic experience.

12.5. IF A COMPOSITE OUTCOME IS USED, DEFINE ALL INDIVIDUAL COMPONENTS OF THE COMPOSITE OUTCOME

In addition to the session-specific tolerability rating, we will ask participants to indicate (if possible) in which 30-second section of a session these side effects occurred. The session-specific tolerability score is defined as the highest tolerability score reported for any present side effects during that block.

13.

TIME SCHEDULE OF ENROLLMENT, INTERVENTIONS, ASSESSMENTS, AND VISITS FOR PARTICIPANTS (A SCHEMATIC DIAGRAM IS HIGHLY RECOMMENDED)

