Pre-trial: Through an online Qualtrics survey: information sheet provided to the participant, consent form, pre-screening and demographic questions, PHQ-9 and M3VAS.

Weeks 1-6: Experimentation, 60 minutes per participant.

Weeks 6+: Data analysis and research and development to create the intervention that will be used in WP2.

14. ESTIMATED NUMBER OF PARTICIPANTS NEEDED TO ACHIEVE STUDY OBJECTIVES AND HOW IT WAS DETERMINED

Based on guidelines for the required sample size for a pilot/feasibility trial to precisely estimate the standard deviation (SD) of a normally distributed variable (session tolerability score) we will use a sample size of 25 (Whitehead et al., 2016). Anticipating a maximum dropout rate of 20% the total sample size required for this study is 32 (WP1).

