To test whether 30-second sections within the strobe sessions are tolerable, participants' maximum tolerability score within each section is considered. If participants don't report any negative symptoms, their tolerability score across the relevant sections will be recorded as 0.

A parameter's 30-second section will be considered tolerable if, across participants, the upper limit of the 80% confidence interval for reported tolerability scores is less than 7.

Secondary outcomes will be evaluated through exploratory analyses, such as examining the frequency of any side effects, engagement, arousal, overall discomfort and enjoyment. These analyses will be descriptive, utilizing data visualizations and descriptive statistics to explore patterns across sessions, both within and between participants.

A1. DESCRIBE ANY PLANNED METHODS TO ACCOUNT FOR MULTIPLICITY IN THE ANALYSIS OR INTERPRETATION OF THE PRIMARY AND SECONDARY OUTCOMES

This is not applicable to this research study.

B. METHODS FOR ANY ADDITIONAL ANALYSES

Secondary outcomes will be explored through data descriptors (i.e. means, standard deviations) and graphs comparing them between sessions within and between participants. Due to expected low power of any such comparisons no inferential statistical analysis will be performed. These explorations will be used to identify potential trends and patterns, but will not be used to infer any relationships between variables.

C. DEFINITION OF ANALYSIS POPULATION RELATING TO PROTOCOL NON-ADHERENCE, AND ANY STATISTICAL METHODS TO HANDLE MISSING DATA

Data from participants who do not attend the experimental testing or withdraw before the administration of any strobe sessions will not be included in the analyses of the intervention's tolerability.

However, if a participant discontinues their participation due to discomfort during the strobe sessions, their partial data up to the point of withdrawal will be included in the analysis.

Data from all participants completing the sign-up form, regardless of their eligibility will be recorded and stored to quantify interest in these strobe light experiments.

The data of any participant requesting their data to be withdrawn from the study, within 2 weeks of the end of testing will be deleted and excluded from all analysis.

METHODS: MONITORING

21.

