In our study, we have established comprehensive procedures for collecting, assessing, reporting, and managing both solicited and spontaneously reported adverse events (AEs) and other unintended effects related to trial interventions or conduct. After each 2-minute strobe session, participants will be prompted to report any discomfort or side effects experienced during the session. They will rate any symptom related discomfort on a scale from 0 to 10. If a participant reports severe symptom discomfort (score >7), testing sessions involving increases of that specific parameter will be halted for that participant to prevent further discomfort, and partial data collected up to that point will be retained for analysis. Any severe adverse clinically relevant events or significant concerns will be promptly reported to the Co-Investigator, [name]. [name] has extensive experience as PI on multiple clinical trials and experimental medicine studies in patients; he has worked as a psychiatrist for 25 years, including 16 years as a consultant (with expertise in affective disorders, psychosis, and liaison psychiatry). Participants will complete the M3VAS and PHQ-9 assessments at the start and end of the experiment to monitor their well-being. If a participant's well-being deteriorates, they will be referred to appropriate mental health services, and [name] will be informed. In rare cases of psychological distress or any concerns from the researchers, [name] will be notified to determine appropriate actions. These procedures are designed to ensure participant safety and comply with regulatory requirements for adverse event reporting in clinical trials.

23. FREQUENCY AND PROCEDURES FOR AUDITING TRIAL CONDUCT, IF ANY, AND WHETHER THE PROCESS WILL BE INDEPENDENT FROM INVESTIGATORS AND THE SPONSOR

All researchers will follow a script and calibrate their conduct periodically through internal reviews.

ETHICS AND DISSEMINATION

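### No symptom rating is scheduled before session 1, so headache, eye discomfort or nausea present on arrival may be scored as a strobe side effect and cannot be separated later

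*Protocol*

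**What the plan says.** The part of the Protocol on interventions for each group (after section 10) sets the timing: "After each 2-minute session, participants will be asked whether they had any side effects". A negative answer closes the matter for that session: "if they select no, they will not be asked any further information regarding the tolerability of the current session". Section 20A then fixes the value for such a participant: "their tolerability score across the relevant sections will be recorded as 0". Section 22 words the prompt more widely: "participants will be prompted to report any discomfort or side effects experienced during the session".

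The items come from three Visual Discomfort Questionnaire (VDQ) "subscales: sickness, eye discomfort and head discomfort" (section 12.1). Each reported symptom is rated 0-10, and section 12.5 adds that "we will ask participants to indicate (if possible) in which 30-second section of a session these side effects occurred".

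Before testing, section 13 lists "information sheet provided to the participant, consent form, pre-screening and demographic questions, PHQ-9 and M3VAS". The interventions part adds the BDI-II, and section 22 places the M3VAS and PHQ-9 at the start and end of the experiment. None of these lists includes a VDQ item or a discomfort rating.

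The primary tolerability outcome is the raw maximum score per 30-second section (sections 12 and 20A). Section 12.2 declares within-participant change not applicable. Of the secondary symptom data, section 12 says that they "will provide early insights into potential mild symptoms that strobe light may cause in individuals with MDD".

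**The concern.** Headache, tired eyes and nausea can be present for reasons unrelated to the light. With one arm and a fixed session order, the only internal reference for such symptoms would be a rating taken before the first exposure, and none is scheduled. The Protocol uses before-and-after measurement for mood, to check that testing has not worsened depressive symptoms, but not for the symptoms that make up its own tolerability score.

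At stake is attribution. The type, frequency and intensity of symptoms are meant as an early indicator for future treatments, and the section scores decide which settings go forward to WP2. Both may include discomfort that the light did not produce. A statistical analysis plan could not supply the missing reference, because it has to be collected at the visit.

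**Working it through.** **1. What is collected before session 1.**

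| Place in the Protocol | Measures before session 1 | Physical symptom rating? |
|---|---|---|
| Interventions for each group | PHQ-9, M3VAS, BDI-II | No |
| Section 13 | Screening, demographics, PHQ-9, M3VAS | No |
| Section 22 | M3VAS, PHQ-9 at the start | No |
| Appendices (safety screening, demographics) | History and eligibility items | No |

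The workflow figure could not be read in the text at hand, so this rests on the written lists.

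**2. Sample size (section 14).** 25 / (1 - 0.20) = 31.25, rounded up to 32. The Protocol's figure reproduces, so n = 25 and n = 32 are used below.

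**3. Possible inflation.** The Protocol gives no background rate. Assume that 10-30% arrive with a symptom rated 2-3. The largest addition to a section mean is prevalence x score:
- low end: 0.1 x 2 = 0.2 points
- high end: 0.3 x 3 = 0.9 points

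These are upper bounds. They require every such symptom to be reported and placed in that section by someone who would otherwise score 0 there. The score is a maximum, so a carried-in 2 or 3 adds nothing where a strobe symptom rates higher.

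On the same assumption, the share with any side effect rises by up to 10-30 percentage points. Each affected participant adds 1/25 = 4 points at n = 25, or 1/32 = about 3 points at n = 32.

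**4. Effect on the decision rule.** Section 20A calls a section tolerable if the upper 80% limit is below 7. I read this as a two-sided t interval for the mean: upper limit = mean + t(0.90, n-1) x SD / sqrt(n). Suppose that only carried-in symptoms are scored and everyone else scores 0.

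Worked case, 5 of 25 scoring 3:
- mean = 15/25 = 0.60
- variance = (5 x 2.4² + 20 x 0.6²)/24 = 36/24 = 1.5
- SE = sqrt(1.5/25) = 0.245
- with t about 1.32, upper limit = 0.60 + 1.32 x 0.245 = 0.92

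| Carried-in symptoms | Mean | Upper 80% limit |
|---|---|---|
| 5 of 25 scoring 3 | 0.60 | 0.92 |
| 8 of 25 scoring 5 | 1.60 | 2.23 |
| 12 of 25 scoring 7 | 3.36 | 4.30 |
| 16 of 32 scoring 7 | 3.50 | 4.32 |

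Even the extreme rows stay well below 7.

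**5. When the decision could change.** At n = 25 a section passes if its mean is below 7 minus the half-width:
- SD 1: 7 - 0.264 = 6.74
- SD 2: 7 - 0.527 = 6.47
- SD 3: 7 - 0.791 = 6.21

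With SD 2 held fixed and the full 0.9 added, only a section with a strobe-only mean between 6.47 - 0.9 = 5.57 and 6.47 could be failed wrongly. In such a section most participants would probably already rate above 3, so the real addition would be smaller still.

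**The case against.** The strongest reply is that the Protocol already filters these symptoms. The gate question asks about side effects, which invites participants to leave out what they arrived with. A negative answer scores 0. Participants say, where they can, in which 30-second section a symptom occurred, and they can comment after each session. Screening removes people with frequent or severe headaches or migraine, discomfort from bright or flickering light, earlier adverse reactions to such light, and listed eye disorders. The secondary outcomes are descriptive only (section 20B), and the causal wording in section 12 is hedged.

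Much of this stands, and it limits the point. It does not remove it. Screening does not cover an occasional headache, tired eyes or nausea on the day. The section 22 prompt covers any discomfort during the session, which includes discomfort that was already there. A descriptive side-effect rate will still be read as a rate of strobe side effects.

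Three stronger readings are tempting, and the documents do not support them:
- A reader might infer that carried-in symptoms are scored automatically in every section. They are not: the gate, the zero rule and the participant's own placement of symptoms all intervene.
- A reader might infer that background symptoms would halt testing. Under the assumed scores of 2-3 they would not, whether the halt is read as above 7 or as 7 and above (the Protocol has both wordings).
- A reader might infer that the choice of control parameters is spoiled. Those are defined by minimal stroboscopic experience (section 7, O2), and separate 0-100 ratings of the experience are taken.

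It is also fair that showing a symptom list early may prompt reports. The fix allows for this.

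**Conclusion.** The point holds as a limit on attribution. Symptoms present on arrival may be counted as strobe effects, and nothing collected later can separate them. It bears mainly on the descriptive type, frequency and intensity of symptoms, and to a lesser degree on section scores. The sizes in steps 3 to 5 rest on the assumed prevalence and severity and on reading the interval as one for the mean. The tolerability decision is unlikely to change, and where it does the error is towards calling a setting less tolerable. This is a worthwhile, inexpensive improvement; it does not invalidate the primary rule.

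**What to change.** In the laboratory, just before session 1, ask once whether the participant has any symptoms now. Use the same yes/no gate as after the sessions, worded for current symptoms, with the same VDQ items and 0-10 rating. Show the list only to those who answer yes, which limits priming.

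Keep the raw section score as the primary outcome. In addition, report section scores and side-effect rates for new or worsened symptoms, meaning symptoms absent at baseline or rated higher than at baseline. Leave the halting checks as they are.

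The cost is one short Qualtrics page, about 1-2 minutes per participant, one more descriptive column, and slight priming among those who see the list early.

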Within the current study, a maximum luminance of 3800 lux over the participant's (closed) eyes at a distance of 1 meter will be used. Previous research has administered stroboscopic light successfully to influence mood states; our research expands this literature by assessing the safety and tolerability of this approach in the MDD population (Johnson et al., 2024).

Participants will undergo 11 stroboscopic sessions of increasing subjective 'intensity', following a fixed order, each lasting 2 minutes. The first 10 sessions are divided into four 30-second sections to test incremental changes in parameters; luminance, stimulation frequency, rapid frequency changes, and duty cycles. Initial sections are designed to induce minimal effects, with subsequent sections using a staircase method to gradually increase the intensity of the stroboscopic experience (see Figure 2). The final session (session 11) will contain a combination of all tested parameters.

| | 1 | 1 | |
|----------------|---------------------------|------------|---|
| Session Number | Tested Parameters | Split | Steps |
| 1 | Luminance | 4 x 30 sec | 10, 30, 50, 70 |
| 2 | Luminance | 4 x 30 sec | 70, 80, 90, 100 |
| 3 | Frequency | 4 x 30 sec | 3, 5, 7, 9 |
| 4 | Frequency | 4 x 30 sec | 9, 11, 13, 15 |
| 5 | Frequency Shift Small | 4 x 30 sec | 3, 3.75, 4.69, 5.82 (multiplicative ratio of 1.25x base Hz, a major third) |
| 6 | Frequency Shift Moderate | 4 x 30 sec | 3, 4.5, 6.75,10.13 (multiplicative ratio of 1.5x base Hz, a perfect fifth) |
| 7 | Frequency Shift Larger | 4 x 30 sec | 3, 6.6, 14.52, 6.6 (multiplicative ratio of 2.2x base Hz, close to a ninth) |
| 8 | Duty Cycle Shift Small | 4 x 30 sec | 50, 55, 60, 65 |
| 9 | Duty Cycle Shift Moderate | 4 x 30 sec | 40, 50, 60, 70 |
| 10 | Duty Cycle Shift Larger | 4 x 30 sec | 25, 50, 75, 50 |
| 11 | Dynamic sequence | 120 sec | Combination of the above parameters |

Figure 2. Individual Stroboscopic Stimulation Session Parameters for Work Package 1.

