As this study is collecting preliminary data to inform the development of a stroboscopic intervention in WP2, we will not be discontinuing the intervention unless requested to by the participant;however, in the case of the current experiment if participants report a tolerability score of 7 or above, thatarm of the study will be halted immediately. If an adverse medical reaction occurs, all testing with that participant will be halted.

C. STRATEGIES TO IMPROVE ADHERENCE TO INTERVENTION PROTOCOLS, AND ANY PROCEDURES FOR MONITORING ADHERENCE

As this is a one-time (1hr) experiment, the adherence will only be monitored within the protocol of the study. Online pre-screening and consent collection ensure informed participation. Researchers will monitor participant experiences throughout testing and offer flexibility in scheduling when needed. Participants receive 10 GBP per hour or SONA credits for engagement with this study.

Experiments are run in the laboratory with a researcher present at all times; participants will be guided and monitored through the entirety of the experiment, guaranteeing the correct administration of the study protocol. All researchers follow an agreed-upon script to reduce researcher bias across the study.

D. RELEVANT CONCOMITANT CARE AND INTERVENTIONS THAT ARE PERMITTED OR PROHIBITED DURING THE TRIAL

Participants undergoing psychotropic treatment or additional talk-based therapeutic interventions are not excluded from participation in this study, but the medication or supplement and self-reported familiarity with their psychotropic treatment will be recorded.

12. PRIMARY, SECONDARY, AND OTHER OUTCOMES, INCLUDING THE SPECIFIC MEASUREMENT VARIABLE, ANALYSIS METRIC, METHOD OF AGGREGATION, AND TIME POINT FOR EACH OUTCOME; EXPLANATION OF THE CLINICAL RELEVANCE OF CHOSEN EFFICACY AND HARM OUTCOMES IS STRONGLY RECOMMENDED

Primary outcome:

- Safety outcomes: no adverse medical incidents (no medical intervention needed)
- Maximum tolerability score per 30 second section (0-10 scale)

Data from Dreamachine suggests a high safety and tolerability profile to stroboscopic stimulation in the general population. However, we need to assess if this is also th case in MDD

The safety outcomes are crucial in assessing the risks of stroboscopic light for people with MDD. If medical intervention is required due to the administration of (certain parameters) of strobe light, their administration will not be appropriate in this population.

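### The severe-discomfort stop depends on a score taken only after each 2-minute session, so up to three 30-second increases can be delivered before it can act, and the protocol does not state this limit

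*Protocol*

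**What the plan says.** The study is a single-arm tolerability study with dose escalation (Protocol, section 8). Under the interventions heading (part A, after section 10), "The first 10 sessions are divided into four 30-second sections to test incremental changes in parameters", "with subsequent sections using a staircase method to gradually increase the intensity of the stroboscopic experience". Figure 2 lists four steps for each of these sessions. Then "The final session (session 11) will contain a combination of all tested parameters".

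**When the score is taken.** "After each 2-minute session, participants will be asked whether they had any side effects". Only participants who answer yes go on to the symptom list and the 0 to 10 discomfort score. Section 12.5 adds that participants will be asked, if they can say, in which 30-second section the effects arose. No score is requested between sections.

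**What the score triggers.** Three places describe it:
- Part A, interventions: any report of a score above 7 "will result in that parameter's testing being stopped immediately to avoid further discomfort".
- Part B, discontinuation: "we will not be discontinuing the intervention unless requested to by the participant"; however, "if participants report a tolerability score of 7 or above", that arm is halted at once. An adverse medical reaction halts all testing for that participant.
- Section 22, adverse events: after a score above 7, "testing sessions involving increases of that specific parameter will be halted for that participant to prevent further discomfort".

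**Other protection.** A researcher attends and monitors throughout and follows a script (part C). Participants may withdraw at any time (section 26A). They sit with closed eyes (part A) in a sound-proof booth (section 9).

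**The concern.** In an escalation study the reader wants to know what stands between one step and the next. Parts A and B give the impression that severe discomfort ends the escalation at once. The measurement that would end it does not exist until all four sections of the session have been given. The score rule therefore cannot interrupt the run of increases that caused the discomfort; it can only withhold what comes later.

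Two things are at stake. First, participants and the ethics committee should be able to see how much further exposure can follow a severe reaction before the rule takes effect. Second, the primary tolerability outcome is the maximum score per 30-second section (sections 12 and 20A), but the section is assigned only afterwards and from memory. An event noted while it happens would serve both purposes.

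**Working it through.** The protocol gives no figure for this point, so the check is a count from Figure 2 set against the rating schedule.

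**Inputs.** Ten sessions of 4 × 30 s = 120 s, with one rating round after each. Families follow the Figure 2 labels: luminance (1, 2), frequency (3, 4), frequency shift (5 to 7) and duty cycle shift (8 to 10). Session 11 is not itemised and is left out of the step counts.

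**1. Steps inside sessions.** There are 10 × 3 = 30 transitions between sections. Sessions 7 (3, 6.6, 14.52, 6.6) and 10 (25, 50, 75, 50) end with a decrease. Upward steps: 8 × 3 + 2 × 2 = 28. All 28 lie inside a session, with no score requested between the two sections.

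**2. Further exposure before the score exists.** If severe discomfort begins in section k, the rest of the session lasts (4 − k) × 30 s.

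| Onset in section | Further exposure | Further increases, 8 sessions | Further increases, sessions 7 and 10 |
|---|---|---|---|
| 1 | 90 s | 3 | 2 |
| 2 | 60 s | 2 | 1 |
| 3 | 30 s | 1 | 0 |
| 4 | 0 s | 0 | 0 |

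**3. What the rating rounds do precede.** At the six boundaries within a family, the setting repeats twice (70 to 70, 9 to 9) and drops four times (5.82 to 3, 10.13 to 3, 65 to 40, 70 to 25). In the shift families, however, the size of the shift is itself escalated across sessions: frequency ratio 1.25, 1.5, 2.2; duty-cycle step 5, 10, 25. Those four enlargements, and the move to session 11, each follow a rating.

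**4. Settings already rated.** Seven of the 28 upward steps start from a setting given in an earlier rated session of the same family:
- 70 to 80 (session 2)
- 9 to 11 (session 4)
- 3 to 4.5 (session 6)
- 3 to 6.6 (session 7)
- 50 to 60 and 60 to 70 (session 9)
- 50 to 75 (session 10)

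The other 28 − 7 = 21 start from a setting not yet rated in that family. If frequency and frequency shift are treated as one parameter, 3 to 3.75 in session 5 is added, giving 8 and 20.

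**5. What is left to withhold.** After sessions 2, 4, 7 and 10 no session with the same label remains. If the parameter named in the rule includes frequency shift, sessions 5 to 7 still remain after session 4; the text does not say. Session 11 contains every parameter, but none of the three statements of the rule says whether it is given. A severe score after session 11 has nothing left to act on.

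**The case against.** The strongest reply is that nothing is misdescribed. Parts A and B tie the word *immediately* to the participant's report, part A gives the rating time in the same paragraph, and section 22 describes the action by session. Read together, the rule is to rate after each session and stop at once on a high score. This stands: a reader might infer a flat contradiction, and the wording does not support one. What remains is that the report cannot exist before the session ends, and the protocol never draws that consequence.

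Three other strong readings also fail.
- *No step is preceded by a check on the one before.* Not so at the level of settings: 7 of 28 steps start from a setting already given in a rated session of the family.
- *Every increase lies inside a session.* True of the listed values in sessions 1 to 10, but not of shift size, which grows from session to session after a rating, nor of the move to session 11.
- *A participant's request is the only trigger during a session.* Part B also halts all testing for an adverse medical reaction, with a researcher monitoring throughout. The gap concerns severe discomfort short of that.

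It can also be said that 90 seconds is short, that rating every 2 minutes is a deliberate choice, and that the script is not shown and may already explain how to signal. These points limit the weight of the concern. They do not remove it: the protocol itself describes no signal for a participant with closed eyes in a sound-proof booth, and neither the researcher's presence nor the right to withdraw is a scored check.

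**Conclusion.** The point holds as an unstated limit on the score-based protection. The rule acts only between sessions. Within a session up to three successive increases, and up to 90 seconds, can follow the onset of severe discomfort before the rule can act; in sessions 7 and 10 it is two increases. After the last session of each labelled family, only sessions outside that family remain, and the status of session 11 is open.

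This rests on the Figure 2 values and labels as printed, and on no score being collected other than as described. The 90 seconds is a maximum: it applies when the participant does not ask to stop and no adverse medical reaction occurs. The documents give no basis for estimating how often this would happen, and no claim is made about that. The matter is worth correcting because the remedy is cheap and the study treats safety in this population as an open question. It does not call the single-session design into question.

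The trigger is also written as above 7 in part A and section 22, but as 7 or above in part B. That is a separate inconsistency, to be reconciled in the same amendment.

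**What to change.** Reconcile parts A and B and section 22 with the rating schedule and Figure 2 on two matters: when the score rule acts, and what it halts (a parameter, an arm, or later sessions that increase the parameter), including whether session 11 is covered.

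Preferably, use the researcher already present and the existing script. Tell participants before each session how to signal discomfort while it is running, and log the time and section of any signal. The log would support the section attribution now asked for only afterwards. What a signal triggers, and the threshold, are for the sponsor to set.

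Otherwise, state plainly in the protocol and the participant information that the score rule acts only after a completed 2-minute session.

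The cost is a script line, a log field and a wording amendment, with no extra staff. If signals lead to sessions ending early, some later sections will be missing for those participants. Sections 20C and 22 already accept partial data, and the log would show where it arose.
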